8.0 Study Calendar

Specific Aims 1 and 3

	Screening	Study Visits 1-4				
	Day 1	Day 2	Day 3	Day 4	Day 5	
STUDY PROCEDURES						
Height	X					
Weight	X	X	X	X	X	

Urine pregnancy		X	X	X	X
Heart rate (electrocardiogram)		X	X	X	X
Arm Blood Pressure	X	X	X	X	X
Core temperature		X	X	X	X
Skin temperature		X	X	X	X
Perceptual scales		X	X	X	X
Bedside shivering scale		X	X	X	X
Surface mechanomyography		X	X	X	X
Resting energy expenditure		X	X	X	X
International Physical Activity Questionnaire (IPAQ)	X				
Health History Questionnaire	X				
Health History Update Questionnaire		X	X	X	X
Infrared Thermography Images		X	X	X	X
PAR-Q+	X				
3-Day Dietary Log		X	X	X	X
Body Composition	X				
Whole Blood		X	X	X	X
Fecal Samples		X	X	X	X

Specific Aim 2

	Screening	Study Visits 1-2	
	Day 1	Day 2	Day 3
STUDY PROCEDURES			
Height	X		
Weight	X	X	X
Urine pregnancy		X	X
Urine Specific Gravity		X	X
Heart rate		X	X
Arm Blood Pressure	X	X	X
Arterial oxygen saturation		X	X
Partial pressure of end tidal CO ₂		X	X
Ventilation		X	X
Core temperature		X	X
Skin temperature		X	X
Perceptual scales		X	X
Bedside shivering scale		X	X
Surface mechanomyography		X	X
International Physical Activity Questionnaire (IPAQ)	X		
Health History Questionnaire	X		
Health History Update Questionnaire		X	X
Infrared Thermography Images		X	X
PAR-Q+	X		
3-Day Dietary Log		X	X
Body Composition	X		

Specific Aim 3

See table for Specific Aims 1 and 3 above.

9.0 Reportable Events

Safety will be constantly monitored during all data collection activities. This will occur on a participant-by-participant basis. If a suspected adverse event occurs in accordance with IU HRPP Policy on Reportable Events, the principal investigator will immediately report to the IRB and cooperate with the IRB in any necessary investigation. All safety data will also be reviewed in weekly lab meetings, particularly as it relates to changes to the risk-benefit ratio.

If any of the following adverse events, which are specific to the procedures conducted in this study, were to occur, they will be immediately reported to the IRB using standard operating procedures.

- Core temperature drops below 35.0°C
- Infection at venous blood draw site
- Loss of confidentiality
- Injury requiring hospitalization and/or activation of EMS.
- Death

Other events deemed as events occurring outside the criteria above will be reported to the IU IRB reported within 5 business days using standard operating procedures. If any event occurs that would potentially impair the health of the participant, the experiment will be halted, and the IRB will be notified.

Any incident, experience, or outcome that meets all the following criteria will also be reported:

- (1) unexpected (in terms of nature, severity, or frequency) given
 - a. the research procedures that are described in the protocol-related documents, such as the IRB-approved research protocol and informed consent document; and
 - b. the characteristics of the participant population being studied;
- (2) related or possibly related to participation in the research (in this guidance document, possibly related means there is a reasonable possibility that the incident, experience, or outcome may have been caused by the procedures involved in the research); and
- (3) suggests that the research places participants or others at a greater risk of harm (including physical, psychological, economic, or social harm) than was previously known or recognized.

Participants will be informed of possible risks before consenting to participate through the informed consent document. Details of foreseeable risks and discomforts for the procedures, and steps taken to lessen the probability and/or magnitude of these risks are noted below.

- Acute Mirabegron ingestion: Mirabegron ingestion in the population that will be studied is deemed safe (3) and will be prescribed under the direction of our study physician, [name]. The doses that will be used in this study have mild cardiovascular (heart rate and blood pressure) effects that are associated with the dose of mirabegron (e.g., the greater the dose of mirabegron, the greater the cardiovascular response (2, 3). Acute oral administration of 200 mg of mirabegron has been shown to increase heart rate by ~8 beats per minute and systolic blood pressure by ~10 mmHg with no changes in diastolic blood pressure (2). These increases in heart rate and blood pressure are far below the heart rate and blood pressure

responses associated with moderate to heavy exercise intensities that are achieved in healthy 18-40 year old men and women.

- Head Out Water Immersion: Water temperature during Specific Aim 2 will be perceived as being cold and rectal temperature will decrease and participants might shiver. We will constantly monitor rectal temperature during the study visits for Specific Aim 2. Any risks are reversible with removal from the cold water and warming with warm water perfused suits and/or mylar blankets, which are located in the laboratory. The protocol will be immediately terminated if core temperature drops to 35.5°C or if the participant does not want to continue. This safety cutoff is 0.5°C higher than the clinical definition of hypothermia and we don't expect core temperature to drop to 35.5°C. For instance, 60 minutes of 15°C water immersion decreased core temperature less than 1°C (8). Another study safely had participants sit in 10°C (50°F) water up to the mid-sternum for 90 minutes and core temperature only decreased to 36.2°C (9). In a case study, 88 minutes of full body immersion in crushed ice lowered core temperature from 37.6°C to 37.0°C (10). Also, the risks associated with hypothermia are core body temperature-dependent and do not appear to be dependent on time (7).
- Whole blood sample: Participants will likely experience discomfort during venous blood draws and in rare circumstances may feel lightheaded or faint. This risk will be minimized by the venipuncture always occurring in the semi-recumbent or supine position. There is a rare risk of infection following venous blood draws. This risk will be minimized by blood draws only being conducted by trained laboratory personnel.
- Rectal temperature: There is an extremely low risk of rectal perforation. This risk will be minimized by using lubricating jelly, while rectal temperature will not be measured in participants with any known chronic (e.g., cancer, surgery, etc) or acute conditions (e.g., diarrhea, constipation, etc.) (or history of disorders) of the rectum. The temperature probe will be self-inserted during instrumentation processes and removed prior to the participant leaving the laboratory. Any risks will be reversed with removal.
- Loss of confidentiality: There is a potential risk for loss of confidentiality. Every effort will be made to keep all subject information confidential. This risk will be alleviated by only using de-identified information.
- Other risks: There may be other risks that we cannot predict.

10.0 Data Safety Monitoring

[name], who is independent from the study, will be responsible for data and safety monitoring. [name] is an experienced environmental physiologist who specializes in thermoregulatory physiology. He is experienced to recognize adverse physiological responses to cold exposure." Data quality, participant recruitment, accrual, retention, outcome and adverse event data will be monitored on a bi-weekly basis.

Data will be monitored by participant number. Thus, analysis of data will be performed without any identifying features to individuals. Statistical software will be used to analyze data for significance. Results will be reported through traditional scientific outlets such as peer-reviewed manuscript and presentations at national and international meetings. Communication with the IRB regarding safety will be reported directly by the principal investigator.

11.0 Study Withdrawal/Discontinuation

Participants can voluntarily withdraw from the study at any time by contacting any of the researchers on the study via any available means (personal contact, email, phone, etc.). If a researcher on the project wishes to withdraw a participant from the study, they will contact the participant directly (personal contact, phone, email, etc.). Possible indications for withdrawal by a researcher include a change in their health history that excludes them from participation and an inability to keep appointments or follow or understand the rules of the protocol. Data collected up to the time of withdraw (either voluntary or by the study team) may be used for analysis.

12.0 Statistical Considerations

Specific Aim 1

Power Analysis: Using data from Loh et al. (2) we expect to observe an effect size (δ) of 0.90 for the comparison of resting energy expenditure in the placebo condition versus 200 mg of mirabegron. Given this effect size, 10 participants will be needed to achieve a power of 0.99 with an alpha level set at 0.05. To account for possible attrition, we plan on recruiting up to 30 participants.

Statistical Approach: We will compare the primary (i.e., thermogenesis) and secondary (i.e., core temperature, skin temperature, heart rate, blood pressure, indices of shivering, thermal perceptions, and infrared thermography images) dependent variables using mixed effects ANOVA (i.e., mirabegron dose x time) followed by Tukey's post hoc procedure if a significant interaction or main effect is found from the ANOVA analyses. We will also calculate the thermogenesis area under the curve for each dose of mirabegron. These values will be compared using repeated measures ANOVA followed by Tukey's post hoc procedure if a significant main effect is found from the ANOVA analysis. We will also perform correlation analyses to determine the relation between body composition and our primary and secondary dependent variables. The alpha level will be set at $P < 0.05$ for all analyses.

Specific Aim 2

Power Analysis: Similar to Specific Aim 1 and the data from Loh et al. (2), we expect to observe an effect size (δ) of 0.90 for the comparison of rectal temperature in the placebo condition versus the mirabegron condition. Given this effect size, 10 participants will be needed to achieve a power of 0.99 with an alpha level set at 0.05. To account for possible attrition, we plan on recruiting up to 30 participants.

Statistical Approach: The primary (i.e., core temperature deflection point) and secondary (i.e., onset of shivering inflection point) dependent variables from the mirabegron and placebo trials will be compared using paired t-tests to determine if mirabegron improves cold-water immersion tolerance. Mixed effects ANOVA will be used to compare the remaining dependent variables between conditions (i.e., mirabegron vs. placebo) and across time. If a significant

interaction or main effect results from the ANOVA analyses, we will use the Holm-Sidak post hoc test to determine where differences exist. The alpha level will be set at $P < 0.05$ for all analyses.

Specific Aim 3

Power Analysis: This aim is being conducted as an exploratory aim in conjunction with Specific Aim 1. As such, to be consistent, we expect to observe an effect size (δ) of 0.90 for the comparison of the gut microbiota in the placebo condition versus 200 mg of mirabegron. Given this effect size, 10 participants will be needed to achieve a power of 0.99 with an alpha level set at 0.05. To account for possible attrition, we plan on recruiting up to 30 participants.

Statistical Approach:

Principal Coordinate Analysis will be performed with group samples and any outliers will be identified. T-tests, and/or ANOVA will be performed to identify significant differences. Statistical analysis to detect variation between samples will be carried out using student t-test or Mann-Whitney test depending on data distribution. Multivariate statistics will be incorporated in a web-based tool Metastats, which can reveal, with high confidence, discriminatory functions between the replicated metagenome dataset of the gut microbiota of humans. In addition, the ShotgunFunctionalizeR and/or Primer E packages will be used for this analysis.

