3.0 Outcome Measures/Endpoints**3.1 Primary Outcome Measures****Specific Aim 1:**

Thermogenesis (i.e., resting energy expenditure) and thermogenesis area under the curve during the protocol. Thermogenesis will be measured using whole body indirect calorimetry, calculated using the Weir formula (5), will be measured every 30 minutes during the 6 hour protocols. Area under the curve for thermogenesis will be calculated to reflect the cumulative effect of mirabegron over time.

Specific Aim 2:

Core temperature deflection point during the progressive cold-water immersion challenge. Core temperature will be continuously measured using rectal thermistors. The point at which core temperature begins to fall (i.e., deflection point) will be identified using Prism 8 software by plotting core temperature vs. water temperature.

Specific Aim 3:

Gut microbiota phylotypes, fecal mirabegron concentration, and serum mirabegron concentration will be measured from samples obtained during the study (serum samples: pre-mirabegron/placebo and following 6 h of mild cold exposure; fecal samples: first bowel movement following 6 h of mild cold exposure). Samples will be assessed using bacterial DNA extraction and purification, polymerase chain reaction, and MinION analysis as well as metabolomics.

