long periods of time in a stable environment. Our whole-body calorimeter is designed to perform human studies that are up to 48 hours in duration and contains a private washroom. While in the whole-body indirect calorimeter, participants will be instructed to be sedentary and will be allowed to watch television or read. In order to stay consistent between study visits, participants will be instructed to spend the same amount of time watching television or reading for each study visit. Every 30 minutes, we will record skin temperatures, core temperature, blood pressure, and heart rate. Thermogenesis will be determined by having participants lie supine for 30 minutes and resting energy expenditure will be calculated using the abbreviated Weir formula every hour (5). Thermal perceptions and an infrared thermography image will also be obtained at these time points. At approximately the midpoint of the 6-hour measurement period, participants will have the opportunity to use the restroom and an additional urine sample will be collected at this time. At the end of the 6-hour measurement period, participants will exit the whole-body indirect calorimeter and final measurements of skin temperature, core temperature, heart rate, and blood pressure will be obtained as well as a final infrared thermography image and a whole blood sample. After the study, participants will be given a mylar blanket to re-warm themselves prior to leaving the laboratory. Participants will be given a fecal collection kit that they will take with them. Instructions will be provided (both verbal and written) on the proper handling of their sample. If participants complete the informed consent/screening visit and all study visits, we expect that they will spend a total of ~33 hours in the study.

Specific Aim 2

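### Section 12.0: power of 0.99 with 10 participants does not follow from δ = 0.90 and alpha 0.05; with δ on the paired-difference SD it is 0.72 (Aim 2) and about 0.55 (Aim 1 AUC)

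*Combined protocol and SAP*

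**What the plan says.** Section 12.0 has a power paragraph for each specific aim. All three take δ = 0.90 and conclude: "Given this effect size, 10 participants will be needed to achieve a power of 0.99 with an alpha level set at 0.05". The allowance beyond 10 is also the same: "To account for possible attrition, we plan on recruiting up to 30 participants". Section 6.0 plans 30 participants for Aim 1 (shared with Aim 3) and 30 for Aim 2. No dropout rate or minimum number of completers is given.

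The endpoints and tests differ between the aims:

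- **Aim 1.** δ refers to resting energy expenditure, placebo versus 200 mg, from a cited acute mirabegron study. Thermogenesis will be analysed as "dependent variables using mixed effects ANOVA (i.e., mirabegron dose x time) followed by" Tukey comparisons. For the area under the curve (AUC), "These values will be compared using repeated measures ANOVA followed by" Tukey comparisons across four conditions.
- **Aim 2.** "we expect to observe an effect size (δ) of 0.90 for the comparison of rectal temperature in the placebo condition versus the mirabegron condition", by analogy with Aim 1. The primary endpoint is the core temperature deflection point, and the primary and secondary "dependent variables from the mirabegron and placebo trials will be compared using paired t-tests".
- **Aim 3.** The same 0.90 is adopted for gut microbiota for the sake of consistency. The aim is labelled exploratory.

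The number of Aim 1 time points is not settled. Section 3.1 says thermogenesis "will be measured every 30 minutes during the 6 hour protocols", while section 7.0 says "resting energy expenditure will be calculated using the abbreviated Weir formula every hour".

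**The concern.** A standardised effect in a crossover trial has no fixed meaning until its SD is named. Scaled to the SD of the paired difference, it gives the power of a paired test directly. Scaled to the SD within a condition, it also needs the within-person correlation. The plan names neither, nor the sidedness or the test. Three aims with different endpoints and tests nevertheless reach the identical result, and one of them borrows an effect size from a different physiological variable.

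The plan uses 0.99 to call 10 participants sufficient and explains the other 20 only as cover for attrition. Taken at its word, a trial that ends with 10 completers is fully powered, and a null result could be presented as near-conclusive. If power at 10 is much lower, that inference fails, and the reader has no means of judging the number who actually complete.

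**Working it through.** **Inputs.** From section 12.0: δ = 0.90, n = 10, alpha 0.05, stated power 0.99. From sections 5.0 and 12.0: Aim 1 has four conditions (placebo, 100, 150 and 200 mg). The SD behind δ, the within-person correlation ρ and the sidedness are not given. They are assumptions below, and tests are two-sided unless noted.

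**Step 1: the plan's figure, with δ on the paired-difference SD (dz = 0.90).**

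*Aim 2, paired t-test.* The noncentrality is dz·√n = 0.90·√10 = 2.846 with df = 9. The two-sided critical value is 2.262 and power is 0.717. One-sided, power is 0.836. Neither gives 0.99.

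*Aim 1 AUC, Tukey contrast of placebo versus 200 mg.* There is one value per condition, with pooled error and sphericity assumed. Error df = 3(n − 1) = 27. The studentized range quantile is 3.870, so the threshold for |t| is 3.870/√2 = 2.737. With the same noncentrality of 2.846, power is 0.551. If the contrast is tested only after a significant ANOVA, as planned, simulation over several dose-response shapes gives about 0.53 to 0.55.

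**Step 2: power by number of completers, same reading.**

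| Completers | Aim 2 paired t | Aim 1 AUC Tukey |
|---|---|---|
| 10 | 0.717 | 0.551 |
| 12 | 0.810 | 0.660 |
| 16 | 0.919 | 0.819 |
| 20 | 0.968 | 0.911 |
| 24 | 0.988 | 0.959 |
| 25 | 0.991 | 0.967 |
| 30 | 0.997 | 0.988 |
| 31 | 0.998 | 0.991 |

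Power of 0.99 needs 25 completers (Aim 2) or 31 (Aim 1), and 0.80 needs 12 or 16.

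**Step 3: δ on the condition SD.** Here dz = 0.90/√(2(1 − ρ)).

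| ρ | dz | Paired t, n = 10 | Tukey, n = 10 |
|---|---|---|---|
| 0 | 0.636 | 0.44 | 0.26 |
| 0.3 | 0.761 | 0.57 | 0.39 |
| 0.5 | 0.900 | 0.72 | 0.55 |
| 0.7 | 1.162 | 0.90 | 0.82 |
| 0.83 | 1.543 | 0.99 | 0.98 |

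At n = 30 the paired t-test has 0.92 (ρ = 0) and 0.98 (ρ = 0.3), and the Tukey contrast has 0.80 and 0.94.

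**Step 4: what would give 0.99 at n = 10.** The dz required is 1.533 (paired t) or 1.643 (Tukey). Solving ρ = 1 − (0.90/dz)²/2 gives 0.828 and 0.850. Alternatively, 0.90 read as Cohen's f gives 0.997 for a four-condition repeated measures ANOVA at ρ = 0. An omnibus F with f = 0.90/2 = 0.45 gives 0.989 for four conditions at ρ = 0.7.

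**Step 5: Aim 1 dose × time model.** Assume that 0.90 is a paired effect at each time point, constant over time, that paired differences correlate r across T time points, and that dose is tested against participant × dose. Averaging over time gives an effective dz = 0.90·√(T/(1 + (T − 1)r)). Six hours at the two stated intervals gives T = 12 or T = 6. Simulated power at n = 10 for the dose main effect followed by Tukey is:

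| r | T = 12 | T = 6 |
|---|---|---|
| 0.9 | 0.58–0.60 | 0.57–0.59 |
| 0.5 | 0.84–0.86 | 0.81–0.83 |
| 0.3 | 0.97 | 0.93–0.94 |

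Setting the effective dz to 1.643 shows that 0.99 needs r of at most 0.24 (T = 12) or 0.16 (T = 6). Power for the interaction was not computed.

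**The case against.** The strongest reply is that no arithmetic error has been proved. The cited study cannot be consulted here, and nothing says δ is on the paired-difference SD. A high within-person correlation, a Cohen's f reading or an omnibus F calculation could each give 0.99 or very nearly so. This stands as far as it goes: true power is not shown to be below 0.99. But none of those inputs is stated. The f reading also sits badly with a quantity called δ for a two-condition comparison, and an omnibus F is not the placebo versus 200 mg comparison that the text names. The stated figure still does not follow from the stated inputs.

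A second reply is that the consequence is limited. With 30 recruited per aim, power on the paired-difference reading falls below 0.80 only with fewer than 12 (Aim 2) or 16 (Aim 1 AUC) completers, and the plan forecasts no such loss. This also stands and keeps the point moderate. It does not remove it, because the plan itself names 10 as enough.

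The dose × time figures rest on modelling choices that the protocol does not make. They show sensitivity, and the conclusion does not need them. Finally, Aim 3 is already called exploratory, and Aim 2 already says that its effect size follows Aim 1. What remains is that 0.99 is offered as a derived power for both, and that Aim 2's power text concerns rectal temperature while its endpoint is the deflection point.

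**Conclusion.** The concern holds. The power of 0.99 at 10 participants does not follow from δ = 0.90 and alpha 0.05 as written. With δ on the paired-difference SD and two-sided tests, the type II error at 10 completers is 0.28 for Aim 2 and about 0.45 for the Aim 1 AUC contrast (the latter assuming sphericity), against a stated 0.01. With δ on the condition SD, the answer at 10 runs from 0.26 to 0.99 across the tests and correlations tried. That range is why the basis must be stated. The point should be fixed, but it does not threaten the trial if completion is close to 30 per aim.

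**What to change.** In section 12.0, state for Aims 1 and 2 the SD to which δ is scaled, the within-person correlation, the test powered and its sidedness. For Aim 1, also state the number of time points, after reconciling sections 3.1 and 7.0. Then recompute power under the planned tests.

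- If the inputs support 0.99 at 10, print them beside it.
- If not, delete the statement that 10 participants give 0.99 and base the justification on the planned 30 per aim, giving power at 10 and at 30 with the assumption named. On the paired-difference SD these would be 0.72 and 0.997 (Aim 2) and 0.55 and 0.988 (Aim 1 AUC Tukey contrast).
- For Aim 2, label 0.90 as an assumption borrowed from resting energy expenditure and not derived for the deflection point.
- For Aim 3, keep the exploratory label and do not present 0.99 as a derived power.

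The cost is wording and one recalculation. Enrolment stays at 30 per aim, but the stated power at 10 will probably look less favourable.
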